### **3. STUDY OBJECTIVE(S) AND ENDPOINTS**

#### **3.1 Study Objective(s)**

Cohort 1: Drug interaction study

Primary objective: To evaluate the drug interactions, safety, and tolerability of sildenafil, rosuvastatin, or furosemide when coadministered with oral edaravone in healthy adult males.

Secondary objective: To evaluate the pharmacokinetics, safety, and tolerability of oral edaravone.

Cohort 2: Preliminary regimen-finding study

Primary objective: To evaluate the effect of food on the pharmacokinetics of oral edaravone in healthy adult males.

Secondary objective: To evaluate the pharmacokinetics, safety, and tolerability of oral edaravone as well as to evaluate effects of racial difference on edaravone pharmacokinetics.

#### **3.2 Safety Assessments**

- Adverse events (AEs) and Adverse Drug Reaction(ADRs)
- 12 lead electrocardiogram (ECG)
- Laboratory tests
- Vital signs
- Sensory tests

#### **3.3 Pharmacokinetics Endpoint(s)/Evaluation(s)**

The pharmacokinetic parameters in plasma will be determined from the individual concentration vs. time data by non-compartmental analysis using WinNonlin® professional version 6.3 or later. The exact sampling time (in hours rounded to 3 decimal places) relative to dosing will be used in calculation. For the calculation of PK parameters concentration below the limit of quantification (BLQ) will be imputed with a value of zero.

##### **3.3.1 Assessments of the Effect on Pharmacokinetics**

- $AUC_{0-24}$ ,  $AUC_{0-\infty}$  and  $C_{max}$  of rosuvastatin, sildenafil, or furosemide alone and in the presence of edaravone
- $AUC_{0-24}$ ,  $AUC_{0-\infty}$  and  $C_{max}$  of unchanged edaravone, sulfate conjugate, and glucuronide conjugate in fasted condition, 1 hour before meal, and 4 hours after meal
- $AUC_{0-24}$ ,  $AUC_{0-\infty}$  and  $C_{max}$  of unchanged edaravone, sulfate conjugate, and glucuronide conjugate in Japanese and Caucasian

### **3.3.2 Analysis of Individual Plasma Concentrations and Pharmacokinetic Parameters**

The pharmacokinetic concentrations over time (individual and mean values) will be assessed for rosuvastatin, sildenafil, or furosemide alone and in presence of edaravone and for edaravone alone and edaravone in the presence of each victim drug (cohort 1); and for unchanged edaravone, sulfate conjugate, glucuronide conjugate in each meal condition and each race (cohort 2).

Following PK parameters will be calculated for each subject and for each treatment:

- In cohort 1, for rosuvastatin, sildenafil, and furosemide alone and in presence of edaravone:  $AUC_{0-t}$ ,  $AUC_{0-24}$ ,  $AUC_{0-\infty}$ ,  $C_{max}$ ,  $t_{max}$ ,  $t_{1/2}$ ,  $Kel$ ,  $MRT$ ,  $CL/F$ ,  $V_z/F$ ,  $V_{ss}/F$
- In cohort 1, for unchanged edaravone, sulfate conjugate (group 2), and glucuronide conjugate (group 2) after administration of edaravone alone and in presence of rosuvastatin, sildenafil, or furosemide:  $AUC_{0-t}$ ,  $AUC_{0-24}$ ,  $AUC_{0-\infty}$ ,  $C_{max}$ ,  $t_{max}$ ,  $t_{1/2}$ ,  $Kel$ ,  $MRT^*$ ,  $CL/F^*$ ,  $V_z/F^*$ ,  $V_{ss}/F^*$  (\* only for unchanged edaravone)
- In cohort 2, for unchanged edaravone, sulfate conjugate, and glucuronide conjugate after administration of edaravone in fasted condition, 1 hour before meal, and 4 hours after meal; or in Japanese and Caucasian:  $AUC_{0-t}$ ,  $AUC_{0-24}$ ,  $AUC_{0-\infty}$ ,  $C_{max}$ ,  $t_{max}$ ,  $t_{1/2}$ ,  $Kel$ ,  $MRT^*$ ,  $CL/F^*$ ,  $V_z/F^*$ ,  $V_{ss}/F^*$  (\* only for unchanged edaravone)

### **3.4 Other Endpoint(s)/Evaluation(s)**

Not applicable in this study.

## **4. PLANNED ANALYSES**

### **4.1 Interim Analysis**

No interim analysis will be performed for this study.

### **4.2 Final Analysis**

Final analysis will be done after database lock as per this SAP. Tables, figures and listings (TFLs) will be prepared by TIT. Acceptance check for the TFLs will be performed by MTPC Data Science Department.

## 5. ANALYSIS POPULATION(S)

The definitions of the analysis sets are provided below. Safety analysis will be performed in the Safety Analysis Set (SAF) and PK analysis will be performed in the PK Analysis Set (PKPOP).

### PK Analysis Set (PKPOP):

- All subjects who received at least 1 dose of the study drug or victim drug and had evaluable PK data.

### Safety Analysis Set (SAF):

- All subjects who received at least 1 dose of the study drug or victim drug.

24 h after dosing (Day 14)	Scheduled time $\pm$ 15 minutes

Edaravone, Sulfate Conjugate, Glucuronide Conjugate	Cohort1 Group2
Pre-dose on Day 3	Before the first dosing of edaravone
0.083h after dosing (Day 3, 6)	Scheduled time $\pm$ 1 minute
0.25, 0.5, 1, 1.5, 2, 4, 6, 8, 12h after dosing (Day 3, 6)	Scheduled time $\pm$ 5 minutes
Pre-dose on Day 4-7	Scheduled time - 15 minutes
24h after dosing (Day 8)	Scheduled time $\pm$ 15 minutes

Edaravone, Sulfate Conjugate, Glucuronide Conjugate	Cohort2
Pre-dose on Day 1, 4, 7	Before dosing of edaravone
0.083 h after dosing (Day 1, 4, 7)	Scheduled time $\pm$ 1 minutes
0.25, 0.5, 1, 1.5, 2, 4, 6, 8, 10, 12h after dosing (Day 1, 4, 7)	Scheduled time $\pm$ 5 minutes
24, 36h after dosing (Day 2, 5, 8)	Scheduled time $\pm$ 15 minutes
48h after dosing (Day 3, 6, 9)	Scheduled time $\pm$ 15 minutes

Rosuvastatin	Cohort1 Group1
Pre-dose on Day 1, 9	Before dosing of Rosuvastatin
0.5, 1, 2, 3, 4, 6, 8, 12h after dosing (Day 1, 9)	Scheduled time $\pm$ 5 minutes
16, 24h after dosing (Day 2, 10)	Scheduled time $\pm$ 15 minutes
48h after dosing (Day 3, 11)	Scheduled time $\pm$ 15 minutes

Sildenafil	Cohodrt1 Group1
Pre-dose on Day 4, 12	Before dogin of Sildenafil
0.25, 0.5, 1, 1.5, 2, 3, 4, 6, 8, 12h after dosing (Day 4, 12)	Scheduled time $\pm$ 5 minutes
24h after dosing (Day 5, 13)	Scheduled time $\pm$ 15 minutes
48h after dosing (Day 6, 14)	Scheduled time $\pm$ 15 minutes

Furosemide	Cohort1 Group2
Pre-dose on Day 1, 6	Before dosing of Furosemide
0.5, 1, 1.5, 2, 3, 4, 6, 8, 12h after dosing (Day 1, 6)	Scheduled time $\pm$ 5 minutes
24h after dosing (Day 2, 7)	Scheduled time $\pm$ 15 minutes
48h after dosing (Day 3, 8)	Scheduled time $\pm$ 15 minutes

## 7. STATISTICAL METHODOLOGY

### 7.1 Statistical Considerations

Prior to database lock, a data review meeting (DRM) was conducted. Protocol deviations, protocol defined analysis populations was confirmed during the meeting. Additional data handling rules was introduced as results of data review.

Only valid PK data will be included in the summary tables or figures. PK data that are considered "invalid" or "abnormal" will be flagged in the listing. The PK data handling will be assessed during DRM prior to database lock.

### 7.3 Sample Size and Power Considerations

- A total of 84 subjects;

Cohort 1: 66 subjects(Group 1: 32 subjects, Group 2: 34 subjects)

Cohort 2: 18 subjects(Japanese 9 subjects, Caucasian 9 subjects)

[Rationales for setting]

(1) Cohort 1

Because there is no information about pharmacokinetic parameters for coadministration of each victim drug (rosuvastatin, sildenafil, or furosemide) and edaravone, the number of subjects for each group was set as follows based on data about  $C_{max}$  and AUC after administration of victim drugs obtained from previous studies and literatures.

- Group 1

Regarding rosuvastatin, based on results of previous studies, geometric CV (intra-

individual) of  $C_{\max}$  and  $AUC_{0-\infty}$  was hypothesized to be 21.0% and 23.0%, respectively. On the assumption that when only rosuvastatin is administered and when it is coadministered with edaravone, ratio of both parameters would be 1.00; the number of subjects was calculated to be 20 which would allow power of at least 80% in 2 one-tailed tests with significance level of 5%.

Regarding sildenafil, based on results of previous studies, geometric CV (intra-individual) of  $C_{\max}$  and  $AUC_{0-\infty}$  was hypothesized to be 28.9% and 22.8%, respectively. On the assumption that when only sildenafil is administered and when it is coadministered with edaravone, ratio of both parameters would be 1.00; the number of subjects was calculated to be 29 which would allow power of at least 80% in 2 one-tailed tests with significance level of 5%.

Based on the above results, the target number of subjects was set at 32, which is the total of 3 (an anticipated number of subjects who might withdraw from the study) and 29 (the number of subjects calculated based on sildenafil data).

- Group 2

Based on results of previous studies, intra-individual geometric CV of  $C_{\max}$  and  $AUC_{0-\infty}$  of furosemide was hypothesized to be 29.5% and 11.5%, respectively. On the assumption that when only furosemide is administered and when it is coadministered with edaravone, ratio of both parameters would be 1.00; the number of subjects was calculated to be 31 which would allow power of at least 80% in 2 one-tailed tests with significance level of 5%. Based on the above results, the target number of subjects was set at 34 on the basis that 3 subjects might withdraw from the study.

Based on the above, the target number of subjects was set at 66 for Cohort 1 (32 for Group 1, 34 for Group 2).

(2) Cohort 2

The target number of subjects was set on the assumption that it would allow obtaining results that will meet the study objectives although it is not based on statistical calculations.

#### **7.4 Disposition of Subjects**

The number and percentage of subjects who completed the study will be presented. Subjects who withdraw will be summarized by reasons for withdrawn.

The number and percent of subjects in each protocol defined analysis set will be presented.

Subject disposition will be listed for all enrolled subjects. Participation in each defined population will be listed.

Whether or not inclusion/exclusion criteria met will also be listed.

## 7.5 Demographic and Other Baseline Characteristics

All demographic data and other baseline characteristics (sex, age, height(cm), weight(kg), BMI, race, medical history, complications, concomitant medications, allergic history (including drug allergies), drinking status, smoking status) will be summarized on the SAF.

A listing of all demographic data and baseline characteristics will be presented for all enrolled subjects.

### (1) BMI

BMI = Body weight (kg) / height (m) (rounded to one decimal place)

Height will be the value obtained at screening.

Body weight will be the value obtained at the time of hospitalization.

## 7.6 Medical History and Complications

All medical history data and complications data will be listed for all enrolled subjects.

## 7.7 Prior or Concomitant Medications

All prior or concomitant medications data will be listed by subject including the ATC level 2 and preferred term.

Prior medications are medications which stopped prior to the first dose of study drug or victim drug.

Concomitant medications are medications which started prior to, on or after the first dose of study medication and ended on or after the date of first dose of study drug or victim drug, or were on-going at the end of the study.

## 7.8 Study Medication Exposure

All study drug and victim drug administration data will be listed.

## 7.9 Pharmacokinetic Assessments

All pharmacokinetic data will be listed on the PKPOP, whether or not the subject has completed all treatment periods. Summaries of concentrations, PK parameters and statistical analysis for rosuvastatin, sildenafil, furosemide, and edaravone and its metabolites will be performed using data from subjects whose PK data will be available in at least one treatment period (e.g. rosuvastatin alone or rosuvastatin + edaravone; edaravone in fasted condition, 1 hour before meal, or 4 hours after meal).

The PK parameters determined by non-compartmental analysis will be listed for the PKPOP. The PK parameters will be calculated using the actual times after dosing (in hours rounded to 3 DP) rather than the nominal times using the reported concentration values. For the

calculation of PK parameters concentration below the limit of quantification (BLQ) will be imputed with a value of zero. All PK parameters will be included in the data listings.

For calculation of AUCs, which is for PK, missing data will be treated as if the respective sample never had been scheduled for the calculation by the linear-linear trapezoidal rule; this has the same effect as if the missing value had been estimated by linear interpolation.

All summaries will be done on the PKPOP and will include the following statistics:

- number of subjects [N]
- number of observations [n]
- Mean
- Standard Deviation [SD]
- Median, Minimum and Maximum
- CV%, where  $CV\% = (SD/\text{mean}) \times 100$
- Geometric mean
- Geometric CV%, where  $Geometric\ CV\% = [\exp(\sigma^2) - 1]^{1/2} \times 100$ , where sigma represents the SD computed on the logarithmic transformed concentration.

For the calculation of the summary statistics for plasma concentrations, concentration values reported as BLQ will be set to zero. For calculation of geometric mean and geometric CV%, LLOQ/2 will be used for values BLQ.

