$\mu\text{mol/L}$. This finding suggests that oral edaravone may cause drug interactions with BCRP substrates by inhibiting BCRP in intestinal epithelial cells. Sildenafil and rosuvastatin are specified as typical substrates of CYP3A and BCRP in the FDA's DDI Draft Guidance. Objective of this group is to assess the effects of multiple doses of edaravone on CYP3A and BCRP activities, with sildenafil and rosuvastatin as the substrates.

Group 2: Sulfate conjugate and glucuronide conjugate of edaravone showed their inhibitory effects on the OAT3 transport activity, with their IC_{50} of $2.74 \mu\text{mol/L}$ and $> 100 \mu\text{mol/L}$ (the remaining transport activity was 67.6% at $100 \mu\text{mol/L}$). This finding suggests that sulfate conjugate and glucuronide conjugate of edaravone may cause drug interactions with OAT3 substrates by inhibiting OAT3. Furosemide is known as an OAT3 substrate. The objective of this group is to assess the effects of the sulfate conjugate and glucuronide conjugate on the OAT3 activity for multiple doses of edaravone, with furosemide as the substrate.

(2) Cohort 2

Crossover study design has been chosen because it allows precise evaluation in a small number of subjects.

In the phase I study (MT-1186-J01 study), when edaravone was administered 30 minutes after a meal, C_{max} and AUC of plasma edaravone decreased to 19.4% and 39.5% of those obtained when it was administered in the fasting state, respectively. When a meal was eaten 30 minutes after edaravone was administered at the same dose, C_{max} and AUC of plasma edaravone decreased to 78.2% and 66.2% of those obtained when it was administered in the fasting state, respectively. For the purpose of finding appropriate administration timing in clinical practice, assessment will be conducted on pharmacokinetics of edaravone obtained when a meal is taken 1 hour after edaravone administration and those obtained when it is administered 4 hours after a meal.

In the phase I study (MT-1186-J01 study), C_{max} and AUC of plasma edaravone in Caucasian subjects were 75% and 79% of those in Japanese subjects, respectively. For the purpose of assessing the difference between races further, a group of Caucasian subjects have been established.

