#### (1) Cohort 1: Drug interaction study

Open-label, add-on study (single dose of a victim drug, multiple doses of an perpetrator drug)

Group 1

	Period I (Dosing: Day 1)	Period II (Dosing: Day 4)	Period III (Dosing: Days 6 to 13)
Victim drugs	Rosuvastatin 10 mg, single dose	Sildenafil 50 mg, single dose	Rosuvastatin 10 mg, single dose (Day 9) Sildenafil 50 mg, single dose (Day 12)
Perpetrator drug	—	—	Edaravone 120mg *) , multiple doses for 8 days (Days 6 to 13)

[figure not shown]
\*) A provisional dose. Doses will be determined based on PK results of MCI-186-J25 study.

Group 2

	Period I (Dosing: Day 1)	Period II (Dosing: Days 3 to 7)
Victim drugs	Furosemide 40 mg, single dose	Furosemide 40 mg, single dose (Day 6)
Perpetrator drug	—	Edaravone 120 mg *) , multiple doses for 5 days (Days 3 to 7)

\*) A provisional dose. Doses will be determined based on PK results of MCI-186-J25 study.

[figure not shown]

(2) Cohort 2: Preliminary regimen-finding study  
Single-dose, open-label crossover study

[figure not shown]
Group	Period I (Dosing: Day1)	Period II (Dosing: Day 4)	Period III (Dosing: Day 7)
3	Edaravone 90mg *) , single dose No breakfast after dosing (3 Japanese and 3 Caucasians)	Edaravone 90mg *) , single dose Start of a meal 1 hour after dosing (3 Japanese)	Edaravone 90mg *) , single dose Dosing 4 hours after breakfast (3 Japanese)
4	Edaravone 90mg *) , single dose Dosing 4 hours after breakfast (3 Japanese)	Edaravone 90mg *) , single dose No breakfast after dosing (3 Japanese and 3 Caucasians)	Edaravone 90mg *) , single dose Start of a meal 1 hour after dosing (3 Japanese)
5	Edaravone 90mg *) , single dose Start of a meal 1 hour after dosing (3 Japanese)	Edaravone 90mg *) , single dose Dosing 4 hours after breakfast (3 Japanese)	Edaravone 90mg *) , single dose No breakfast after dosing (3 Japanese and 3 Caucasians)

\*) A provisional dose. Doses will be determined based on PK results of MCI-186-J25 study.

Japanese subjects :

Caucasian subjects :

(3) Study Period and Evaluation Period

Study period: The study period is defined as the period from informed consent to completion of the end-of-study assessment (or to completion or termination of follow-up, for any followed-up subjects).

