#### *PK Parameters*

The following PK parameters for unchanged edaravone, sulfate conjugate and glucuronide conjugate will be calculated from measured plasma concentrations:  $AUC_{0-t}$ ,  $AUC_{0-24}$ ,  $AUC_{0-\infty}$ ,  $C_{max}$ ,  $t_{max}$ ,  $t_{1/2}$ ,  $Kel$ ,  $MRT^*$ ,  $CL/F^*$ ,  $V_z/F^*$ ,  $V_{ss}/F^*$  (\* only for unchanged edaravone)

The PK parameters will be listed. Summary statistics (N, n, mean, SD, median, minimum, maximum, geometric mean and geometric CV%) will be presented for all PK parameters by treatment (edaravone in fasted condition, or before or after meal) and race (Japanese or Caucasian).

These parameters will also be listed. For all PK profiles for which the  $Kel$  has been calculated, the following will be listed:

- Number of data points used in the regression analysis for estimation of  $Kel$ .
- The lower and upper limits of the time period spanned by the data points used in the regression analysis for estimation of  $Kel$ .
- Adjusted R-squared value.
- Percentage of  $AUC_{0-\infty}$  extrapolated.

For  $C_{max}$ ,  $AUC_{0-t}$ ,  $AUC_{0-24}$  and  $AUC_{0-\infty}$  spaghetti plots or scatter plots will be produced showing individual differences between fasted condition and administration before or after meal, and showing differences in parameter distributions of Japanese and Caucasian subjects.

For  $C_{max}$ ,  $AUC_{0-t}$ ,  $AUC_{0-24}$  and  $AUC_{0-\infty}$  ratios (administration before or after meal/ fasted condition in Japanese subjects) will be calculated for each subject. These will be listed and summary statistics (N, n, mean, SD, median, minimum, maximum) for these will also be presented.

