#### **7.9.5 Assessments of effect of meal conditions on pharmacokinetics of Unchanged Edaravone, Sulfate Conjugate, and Glucuronide Conjugate**

PK parameters  $AUC_{0-\infty}$  and  $C_{max}$  of unchanged edaravone, sulfate conjugate, and glucuronide conjugate for each meal condition will be analysed for the assessments of effect on pharmacokinetics of unchanged edaravone, sulfate conjugate, and glucuronide conjugate by meal conditions.

*Descriptive Statistics:*

Pharmacokinetic parameters will be summarized by analyte (i.e. unchanged edaravone, sulfate conjugate, and glucuronide conjugate) in fasted condition, 1 hour before meal, and 4 hours after meal.

*Statistical Analysis:*

A linear mixed effects model will be fitted to log-transformed PK parameters ( $AUC_{0-t}$ ,  $AUC_{0-24}$ ,  $AUC_{0-\infty}$ , and  $C_{max}$ ) including meal condition, period and group as fixed effect and subject as random effect. Meal condition will be in fasted condition, 1 hour before meal or 4 hours after meal. Estimates of mean difference between fasted condition and before or after meals will be obtained with 90% CI for the difference. These estimates and limits will then be back-transformed to obtain ratios of least squares geometric means A 90% CI for the ratio of  $AUC_{0-\infty}$  as well as  $C_{max}$  which lie entirely within the limits of 0.80 to 1.25 provides evidence of no effect of food intake on unchanged edaravone, sulfate conjugate, and glucuronide conjugate.

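### As written, the Cohort 2 food-effect model takes in nine Caucasian subjects dosed only fasted and has no race term, so a race difference would bias both fed/fasted ratios

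*SAP*

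**What the plan says.** Four parts of the SAP decide which records enter the food-effect model.

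- **Analysis set (section 5).** PKPOP is "All subjects who received at least 1 dose of the study drug or victim drug and had evaluable PK data". It has no limit by race.
- **Record rule (7.9).** Summaries and statistical analysis for the victim drugs and for edaravone and its metabolites are "performed using data from subjects whose PK data will be available in at least one treatment period". The examples that follow include edaravone in the fasted condition.
- **Design (2.2.1, Cohort 2 table).** Groups 3, 4 and 5 each have 3 Japanese subjects who cross over all three meal conditions and 3 Caucasian subjects dosed once, fasted.
- **Model (7.9.5).** A mixed model on log parameters, "including meal condition, period and group as fixed effect and subject as random effect". Food is declared to have no effect if the 90% CIs for AUC0-∞ and Cmax lie within 0.80 to 1.25.

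Protocol 13.4.2 specifies the same model structure and also does not mention race. Race is modelled only in SAP 7.9.6.

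**The concern.** A Caucasian subject with one fasted profile meets the 7.9 rule, belongs to PKPOP, and has a value for every term in the 7.9.5 model. A programmer following the text would include that record, and nothing in the model separates race from meal condition.

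The food effect is the primary objective of Cohort 2. If Caucasian exposure is lower, the fasted reference is pulled down and both fed/fasted ratios rise. A real loss of exposure with food then looks smaller and is more easily declared absent, while a true ratio of 1.00 is moved away from 1. If Caucasian exposure is higher, the ratios fall. The issue is bias in the estimate and in the decision rule, not power, since Cohort 2 was not sized by calculation (SAP 7.3).

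**Working it through.** Neither document gives a sample-size, power or precision figure for Cohort 2, so there is no plan figure to reproduce.

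**Inputs from the documents**
- Records: 9 Japanese × 3 conditions = 27, plus 9 Caucasian fasted, total 36. All 18 fed records are Japanese; 9 of the 18 fasted records are Caucasian.
- Race ratio R (Caucasian/Japanese), unchanged edaravone, prior oral study (Protocol section 1 (3)): Cmax 0.75, AUC 0.79. The IV population analysis in the same section found no particular difference, which corresponds to R = 1. No ratio is given for the two conjugates, so no factor is computed for them.

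**Assumptions**
- The documents give no CV for edaravone. Between-subject CV of 20, 30 and 40% and within-subject CV of 15, 20 and 30% are assumed, with log variance s² = ln(1 + CV²) and ρ = s²(between) / [s²(between) + s²(within)].
- R = 1.333 (1/0.75) is included only to show the opposite direction.

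**Step 1: weight given to the Caucasian records.** They sit in the same group-by-period cells as the Japanese fasted records, so period and group can be set aside. Let the fasted reference be (1−w) × Japanese mean + w × Caucasian mean. The variance of fed minus reference, in units of total variance/9, is

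1 + (1−w)² + w² − 2(1−w)ρ.

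Setting the derivative to zero gives w = (1−ρ)/2. Each fed/fasted ratio is therefore multiplied by exp(−(1−ρ)/2 × ln R). Generalised least squares on the full 36-record design, with period and group included, gives the same factor for both fed conditions.

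**Step 2: size of the bias**

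| CV between/within | s² between | s² within | ρ | w | Factor, R = 0.75 | Factor, R = 0.79 |
|---|---|---|---|---|---|---|
| 30%/20% | 0.0862 | 0.0392 | 0.687 | 0.156 | 1.046 | 1.038 |
| 20%/30% (largest) | 0.0392 | 0.0862 | 0.313 | 0.344 | 1.104 | 1.084 |
| 40%/15% (smallest) | 0.1484 | 0.0223 | 0.870 | 0.065 | 1.019 | 1.015 |

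Example, first row: exp(0.156 × 0.2877) = 1.046. With variances estimated by REML the range over the grid is 1.015 to 1.096. At R = 1.333 the factor is 0.906 to 0.981. At R = 1 it is exactly 1.

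**Step 3: effect on the decision rule.** Simulation with REML, 20,000 trials per setting, t with 14 df, meal 1 hour after dosing against fasted. The entries are the chance that the 90% CI lies within 0.80–1.25.

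| True ratio | R | CV between/within | All 18, no race term | Japanese only |
|---|---|---|---|---|
| 0.80 | 0.75–0.79 | 30%/20% | 9.3–10.1% | 5.0% |
| 0.80 | 0.75–0.79 | whole grid | 2.7–14.6% | 1.7–5.2% |
| 0.80 | 0.75–0.79 | 20%/30% | 4.4–4.7% | 1.8% |
| 1.00 | 0.75 | 20%/15% | 76.8% | 83.4% |
| 1.00 | 0.75 | 30%/20% | 48.0% | 47.2% |

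At a true ratio of 0.80 and R = 1.333, the all-18 figure falls to 0.9–3.4%.

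**Step 4: the two remedies.** Restricting to Japanese subjects or adding a race term removes the bias at every ρ. Both have standard error √(2 × s²(within)/9); at 30%/20% this is √(2 × 0.0392/9) = 0.0934. The pooled model without race has √{(0.1254/9) × [2 × 0.3128 − 0.3128²/2]} = 0.0896. The increase is 0.0934/0.0896 = 1.042, and over the grid about 2 to 10%. Error df are unchanged: 27 − 9 − 2 − 2 = 14 and 36 − 18 − 2 − 2 = 14.

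**The case against.** The strongest reply is that a Japanese-only food analysis was plainly meant, and that the filter may sit in text that could not be read.

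- On purpose, Protocol 5.2.1.3 says: "For the purpose of assessing the difference between races further, a group of Caucasian subjects have been established". SAP 3.3.2 lists meal and race as alternative comparisons ("4 hours after meal; or in Japanese and Caucasian"). SAP 7.9.4 limits the individual fed/fasted ratios to Japanese subjects, and 7.10.1 tabulates the two races separately.
- SAP section 8 justifies the wider PKPOP by incomplete victim-drug subjects, so the 7.9 rule may have been aimed at missing data.
- Read with equal literalness, 7.9 would also bring Cohort 1 fasting profiles into 7.9.5, and fed Japanese records into 7.9.6. Nobody would do that.
- SAP 7.2 (Data Handling) and the example SAS code were not readable, and 7.1 adds: "Additional data handling rules was introduced as results of data review". Those rules are not shown either.
- The size rests on assumed CVs. The largest factor needs within-subject variability above between-subject variability, and there the false no-effect rate stays below 5%. Cohort 2 is preliminary.

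Most of this stands as evidence of intent, and it is why the point is conditional. It does not settle the matter. None of these passages governs the 7.9.5 model. Section 7.9.4 names Japanese subjects for a descriptive ratio, while the model that carries the decision does not. The 7.9 rule names the edaravone meal conditions, so its wording reaches beyond victim-drug dropouts. Section 7.9.6 at least implies one record per subject, because its linear model has race alone and no subject term; 7.9.5 contains no comparable signal.

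**Conclusion.** The concern holds on the readable text. Followed as written, the plan pools 9 fasted-only Caucasian subjects into the fasted reference of the Cohort 2 primary comparison without a race term. At the race ratios the protocol itself reports, both fed/fasted ratios for unchanged edaravone are inflated by 1.5% to 10.4% over the assumed CVs, and by 3.8% to 4.6% at 30%/20%, where the false no-effect rate at a true ratio of 0.80 roughly doubles. The bias is modest, changes direction if Caucasian exposure is higher, and disappears if there is no race difference.

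Confidence is moderate for two reasons: the edaravone CVs are assumed, and SAP 7.2, the data-review rules or the SAS code may already restrict the records.

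**What to change.** In SAP 7.9.5, state that the food-effect model uses only the Japanese crossover subjects (27 planned records), or add race as a fixed effect, and make the example SAS code match. If 7.2 or the code already does this, a cross-reference in 7.9.5 is enough. As a minor clarification, 7.9.6 should say that one fasted record per subject is used (9 against 9).

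The cost is one sentence in each section and a data filter or one model term, plus the small loss of precision in Step 4. Both options give the same standard error, and the simulated no-effect rates with a race term are within 0.3 percentage points of the Japanese-only analysis.
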